2.0 Schedule of Visits

Study Visit	Screening	Baseline	Follow up visits	
	Within 60 days of baseline	Visit 1	Visit 2 (12 months after visit 1) HIV positive cohorts only	Visit 3 (24 months after visit 1)
Informed Consent	x			
Review Eligibility	x	x		
Detailed medical history as per protocol		x	x	x
Study Questionnaire		x	x	x
Respiratory questionnaire				x
Neurocognitive assessment		x		x
DXA scan			x	
Blood sampling		x		x
Phone contact			x (HIV negative cohort)	x

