4.1 Study population

Inclusion Criteria

Older HIV-positive cohort (n=1000):

- documented HIV infection
- age ≥ 50 years at study entry
- self defined white or black African ethnicity
- likely route of HIV acquisition via sexual exposure
 - Either by male to male exposure if white or by heterosexual exposure if white or black African
- able to comprehend study patient information leaflet

Subjects with primary HIV infection are eligible and investigators are encouraged to recruit such subjects.

Our target population (those of white or black African ethnicity and those infected with HIV via sexual routes) has been chosen as these groups represent the vast majority of older HIV-positive individuals attending for care in the UK; analyses of other groups (e.g. injection drug users, those infected through blood/blood products and transgender individuals), who may have very different needs and outcomes, would likely be under-powered.

Younger HIV-positive cohort (n=500):

- documented HIV infection
- age < 50 at study entry*
- self defined white or black African ethnicity
- likely route of HIV acquisition via sexual exposure
 - Either by male to male exposure if white or by heterosexual exposure if white or black African.
- able to comprehend study patient information leaflet

* this group will comprise of at least 150 subjects in each of the following age groups: 20-29, 30-39, 40-49 years. Recruitment will be monitored by the Study Monitoring Team

HIV-negative cohort (n=500):

- documented negative HIV test at screening
- age ≥ 50 years at study entry
- self defined white or black African ethnicity
- registered with a General Practitioner and gives permission for contact with that GP.

Exclusion Criteria

- in the opinion of the investigator, those unable or unwilling to comply with the requirements of the study
- life expectancy less than 6 months

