5.3 Visit 2 (1st year follow up visit)

This follow up visit will be performed as per schedule of visits (2.0).

Only HIV-positive cohorts will be invited to undertake this visit with this visit expected to take 1 hour.

The following will be assessed:

- Changes to lifestyle and socio-economic status over the past year.
- Significant clinical events occurring over the past year: dates of onset and resolution, use of medical services, changes to antiretroviral and other medications, and resulting ongoing health concerns.
- Blood pressure will be estimated using an automated device.
- Details of access to health care services over the past year: visits to the general practitioner, hospital, counselors, psychiatrists, psychologists and medical investigations performed (information obtained by direct questioning and through HIV note review). Permission will be sought to contact the patient's general practitioner and/or hospital for further details.

- Most recent laboratory tests will be recorded: renal, liver, lipid and bone profiles, glucose, full blood count, sexual health screen, hepatitis C serology (Within the past year)
- Concomitant medications: start/stop dates; dose; dosing frequency; side effects.
- Fracture occurrence and fracture risk (see study questionnaire in appendix 1)
- Regional and widespread pain.

5.3a Visit 2 (1st year follow up visit) for HIV negative participants.

These participants will be contacted by telephone by arrangement with the study nurse. They may be asked to attend the clinic in order to facilitate this visit.

Details of any changes in circumstances or illnesses and medication will be documented.

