5.4 Visit 3 (2nd year follow up visit)

This follow up visit will be performed as per schedule of visits (2.0).

This visit is expected to take 1-2 hours; if possible the subject should attend fasted. The following information will be collected:

- Changes to lifestyle and socio-economic status over the past year.
- Significant clinical events occurring over the past year: dates of onset and resolution, use of medical services, treatments, and resulting ongoing health concerns.
- Details of access to health care services over the past year: visits to the general practitioner, hospital, counselors, psychiatrists, psychologists and medical investigations performed (information obtained by direct questioning and through HIV note review). Permission will be sought to contact the patient's general practitioner and/or hospital for further details.
- Measurement of hand grip strength using an automated device.
- Simple measurement of walking speed over a distance of 15 feet (457 cms).
- Blood pressure will be estimated using an automated device.
- Concomitant medications: start/stop dates; dose; dosing frequency; side effects.
- Fracture occurrence and fracture risk (see study questionnaire in appendix 1).
- DXA scan for bone mineral density (full body DXA where available) (within 30 days of clinic appointment)
- Neurocognitive function: specific memory and cognitive testing assessing cortical and sub-cortical function.
- Respiratory questionnaire
- Regional and widespread pain.
- Quality of life questionnaire.
- Most recent laboratory tests will be recorded (assessed in the HIV-negative cohort): renal, liver, lipid and bone profiles, glucose, full blood count, sexual health screen, hepatitis C serology (within the previous year)
- Blood (serum, plasma, and PBMC) and urine samples: stored for subsequent projects of the potential pathogenic mechanisms underlying age-related diseases. This will include assessment of vitamin-D and PTH
- Blood (plasma) will be collected for pharmacokinetic analysis (including but not limited to antiretroviral drug exposure)

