7.1.2 Serious Adverse Events (SAE)

A SAE is any untoward medical occurrence or effect that:

- **Results in death**
- **Is life-threatening – refers to an event in which the subject was at risk of death at the time of the event; it does not refer to an event which hypothetically might have caused death if it were more severe**
- **Requires hospitalisation, or prolongation of existing inpatients' hospitalisation**
- **Results in persistent or significant disability or incapacity – there is a substantial disruption of a person's ability to carry out normal life functions**
- **Is a congenital abnormality or birth defect**

An SAE form should be completed and faxed to ICTU for all SAEs within 24 hours of notification about the event. The ICTU will inform the following individuals within 24 hours of receiving notice of them:

1. The Sponsor (JRO, Imperial College London)

Sponsor:Imperial College London Sponsor No:CRO1992	Version 18.0	Page 18 of 44
---	--------------	---------------

2. Funders where contractually agreed
3. The Chief Investigators ([name] and [name])

Given the observational and non-interventional nature of this study, no additional information on SAEs will be captured.

At the study baseline visit, any SAEs occurring during the one year period leading up to entering the study will be assessed. Thereafter, at each yearly visit, SAEs occurring over the past year will be recorded.

All SAEs and AEs will be recorded on the annual study reports that are sent to the MHRA and REC.

Also, given the observational and non-interventional nature of this study, no serious, unexpected adverse drug reactions (SUSARs) reporting will be undertaken. As all subjects continue with their general clinical care, which is unaltered during the course of this study, the 'yellow card' reporting will be unaffected.

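### Year-1 event capture is specified more fully for the HIV-positive cohorts than for the HIV-negative cohort, so incidence comparisons of non-serious events, chiefly non-hospitalised fractures, may be biased towards an HIV effect by an unknown, possibly nil, amount

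*Combined protocol and SAP*

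**What the plan says.** Section 5.3 gives the HIV-positive cohorts a one-hour clinic visit at year 1. The listed items include significant clinical events with onset and resolution dates, health-care use (by questioning and HIV note review), recent laboratory results, and "Fracture occurrence and fracture risk (see study questionnaire in appendix 1").

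Section 5.3a covers the HIV-negative cohort. Participants are telephoned, and the content is one sentence: "Details of any changes in circumstances or illnesses and medication will be documented". Clinic attendance is optional: "They may be asked to attend the clinic in order to facilitate this visit". The Schedule of Visits (2.0) heads the column "Visit 2 (12 months after visit 1) HIV positive cohorts only" and shows a phone contact for the HIV-negative cohort.

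Visit 3 (section 5.4) applies to all cohorts. Its event item reads "Significant clinical events occurring over the past year: dates of onset and resolution, use of medical services, treatments, and resulting ongoing health concerns". It has a fracture item without a time window. Health-care use is again "information obtained by direct questioning and through HIV note review".

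Three provisions bear on the HIV-negative cohort's capture. Section 7.1.2 states "Thereafter, at each yearly visit, SAEs occurring over the past year will be recorded", without restriction by cohort. Section 4.1 requires HIV-negative participants to be "registered with a General Practitioner and gives permission for contact with that GP". Section 8.1 opens by saying that detailed clinical-event information is gathered at baseline and every visit, and it makes no exception by cohort.

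Section 8.1 then plans logistic or Poisson regression to compare prevalence and incidence where numbers allow. It expects 105 incident fractures and 100 cases of chronic kidney disease.

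**The concern.** A comparison of incidence between cohorts assumes that an event of a given kind is equally likely to be counted in each. Here the year-1 prompts, setting and record sources differ by HIV status, which is the exposure being compared. If the open phone question elicits fewer events than the listed clinic items, the HIV-negative count falls and the HIV-positive versus HIV-negative ratio rises with no true difference behind it.

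Visit 3 would repair this if it asked about the whole period since baseline. As worded, its event item leaves the first year out and its fracture item leaves the period open.

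Fractures are the outcome most exposed. They are one of only two incident outcomes expected to reach about 100 events, and many need not meet a seriousness criterion. Section 3.5 presents the matched HIV-negative group as what allows effects of HIV to be separated from effects of ageing, and section 4.3 sets out to describe incidence of fragility fractures in all three cohorts. Section 8.1 has no step to check or adjust for unequal capture.

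**Working it through.** **The plan's own figure.** The 105 fractures cannot be reproduced, because no fracture rate, person-years or loss to follow-up is given. That they belong to the HIV-positive cohorts is inferred from the preceding sentence in section 8.1. On that reading they are 105/1500 = 7.0% of the planned HIV-positive participants, or 105/1350 = 7.8% of the base implied elsewhere in 8.1 (540/0.40 = 1350).

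**Inputs.**
- HIV-positive fractures: 105 (section 8.1, attribution inferred).
- HIV-negative fractures expected at the same rate: 105 × 500/1500 = 35. The other base with 450 controls gives the same: 105 × 450/1350 = 35.
- Assumed, not in the documents: equal true rates, half of events in year 1, full capture in the HIV-positive cohorts, and equal capture in year 2.
- h = share of fractures that are serious adverse events and so captured equally. Not in the documents; shown at 0, 0.25, 0.5 and 0.75.
- s = share of non-serious year-1 fractures captured by phone, relative to clinic. Not in the documents.
- r = share of the missed fractures recovered at Visit 3. Not in the documents.

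**Formulas.** Fraction of HIV-negative fractures counted: f = 1 − 0.5 × (1 − h)(1 − s)(1 − r). Apparent ratio = 1/f. SE of the log ratio = √(1/105 + 1/(35f)). z = ln(1/f)/SE. The two-sided false-positive rate is P(Z > 1.96 − z) + P(Z < −1.96 − z), for an unadjusted 5% test.

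**Half of non-serious year-1 fractures missed, none recovered (s = 0.5, r = 0).**

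| h | f | Counted HIV-negative | Ratio | SE | z | False positives |
|---|---|---|---|---|---|---|
| 0 | 0.75 | 26.25 | 1.33 | 0.218 | 1.32 | 26% |
| 0.25 | 0.8125 | 28.4 | 1.23 | 0.211 | 0.98 | 17% |
| 0.5 | 0.875 | 30.6 | 1.14 | 0.205 | 0.65 | 10% |
| 0.75 | 0.9375 | 32.8 | 1.07 | 0.200 | 0.32 | 6% |

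**Smaller loss, or some recovery.**
- h = 0, r = 0: s = 0.9 gives ratio 1.05 and 5.8%; s = 0.7 gives 1.18 and 12.3%.
- h = 0, r = 0.5: s = 0.9, 0.7, 0.5 give ratios 1.03, 1.08, 1.14 and rates 5.2%, 6.7%, 10.0%.
- r = 1, any s and h: f = 1, ratio 1.00, rate 5%.

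A simulated Wald test on Poisson counts with h = 0 and r = 0 gives 5.1%, 10.8% and 24.3% for s = 0.9, 0.7 and 0.5, so the normal approximation runs slightly high.

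**Precision of a year-2-only analysis.** With half the events (52.5 v 17.5), the 95% CI factor is exp(1.96 × √(1/52.5 + 1/17.5)) = exp(1.96 × 0.276) = 1.72. For 105 v 35 it is exp(1.96 × 0.195) = 1.47.

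**The case against.** The strongest reply is that section 8.1 promises detailed event information at every visit, and both the synopsis and section 5.3a treat the phone contact as Visit 2. On that reading the protocol does commit to detailed collection in HIV-negative people, and the gap is an unspecified phone form. This stands in part. The phone form and the electronic case report form are not in the documents, so a reader might infer a settled plan to collect less from HIV-negative people, and the text does not show that. But the general promise in 8.1 is not carried into 5.3a, which is the section that staff would follow.

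Second, yearly recording of serious adverse events covers hospitalised fractures in every cohort. This stands and confines the risk. A reader might take the 26% figure as the likely error rate for fractures. It assumes that no fracture is serious, half of year-1 fractures are missed and none are recovered; the documents support none of these values.

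Third, the fracture contrast is not fully visible. The item points to Appendix 1, where the only visible broken-bone question follows one about falls in the past 28 days, and some figures are not shown. So the documents do not settle how much better the clinic item performs, or whether Visit 3 recovers the first year. A phone call might also reach more people than a clinic visit. The direction is therefore expected, not proven.

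Fourth, the consequence is bounded. Many analyses are descriptive, and no fracture comparison is named. Incidence of myocardial infarction, malignancy and liver failure is descriptive only. Persistent chronic kidney disease would be found at 24 rather than 12 months in HIV-negative people, so it is delayed and not lost. Older versus younger HIV-positive comparisons are unaffected. All of this stands.

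The permission for GP contact and the optional clinic attendance help less, because 5.3a specifies no GP check and no rule for when attendance is requested.

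**Conclusion.** The concern holds in a limited form. Followed as written, the protocol specifies fuller year-1 event capture for the HIV-positive cohorts, does not assure recovery at Visit 3, and plans incidence comparisons across that difference. The risk concerns non-serious events, chiefly non-hospitalised fractures, in HIV-positive versus HIV-negative comparisons. The expected effect is an inflated ratio.

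The size cannot be fixed from the documents and may be nil. In the illustrated scenarios the ratio runs from 1.00 to 1.33 and the false-positive rate from 5% to 26%. These rest on the inferred attribution of the 105 fractures, an even split of events between years, equal true rates, and assumed values of h, s and r. The documents do not support a claim that the fracture comparison will be false, or that all incident outcomes are affected. The change is worth making because it is cheap and because events not recorded comparably are hard to repair at analysis. Confidence is medium.

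**What to change.** 1. In section 5.3a, use the same structured, dated event form as in 5.3, with explicit prompts for fractures and major conditions. If the phone form already does this, say so in 5.3a.
2. In section 5.4, state one look-back for the event and fracture items in all cohorts: since the last completed study contact, or since baseline where Visit 2 has already taken place. The second wording matters because this is version 18.0 and recruitment is well advanced at some sites, so the phone contact may be past for many participants.
3. Where Visit 2 is past, add a sensitivity analysis of HIV-positive versus HIV-negative incidence limited to year-2 events, using only items asked the same way in all cohorts. HIV note review is used again at Visit 3 and no field for the source of an event is described, so the analysis should rest on the common items and not on removing note-review events afterwards.

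The cost is a form amendment, a slightly longer call and somewhat longer recall. The year-2 analysis is less precise (95% CI factor about 1.72 rather than 1.47), so it should support the main comparison and not replace it.

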5.4 Visit 3 (2nd year follow up visit)

This follow up visit will be performed as per schedule of visits (2.0).

This visit is expected to take 1-2 hours; if possible the subject should attend fasted. The following information will be collected:

- Changes to lifestyle and socio-economic status over the past year.
- Significant clinical events occurring over the past year: dates of onset and resolution, use of medical services, treatments, and resulting ongoing health concerns.
- Details of access to health care services over the past year: visits to the general practitioner, hospital, counselors, psychiatrists, psychologists and medical investigations performed (information obtained by direct questioning and through HIV note review). Permission will be sought to contact the patient's general practitioner and/or hospital for further details.
- Measurement of hand grip strength using an automated device.
- Simple measurement of walking speed over a distance of 15 feet (457 cms).
- Blood pressure will be estimated using an automated device.
- Concomitant medications: start/stop dates; dose; dosing frequency; side effects.
- Fracture occurrence and fracture risk (see study questionnaire in appendix 1).
- DXA scan for bone mineral density (full body DXA where available) (within 30 days of clinic appointment)
- Neurocognitive function: specific memory and cognitive testing assessing cortical and sub-cortical function.
- Respiratory questionnaire
- Regional and widespread pain.
- Quality of life questionnaire.
- Most recent laboratory tests will be recorded (assessed in the HIV-negative cohort): renal, liver, lipid and bone profiles, glucose, full blood count, sexual health screen, hepatitis C serology (within the previous year)
- Blood (serum, plasma, and PBMC) and urine samples: stored for subsequent projects of the potential pathogenic mechanisms underlying age-related diseases. This will include assessment of vitamin-D and PTH
- Blood (plasma) will be collected for pharmacokinetic analysis (including but not limited to antiretroviral drug exposure)

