5.6 Study timelines

Recruitment and baseline visits (visit 1) will take place from months 1-12, with annual visits from months 13-24 (visit 2) and 25-36 (visit 3)

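### The fixed one-year look-back for clinical events, health-care use and SAEs leaves follow-up time unasked after a missed year-1 contact or a late visit

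*Combined protocol and SAP*

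**What the plan says.** Three places fix the look-back at one year:

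- Section 5.4 (Visit 3, all cohorts): "Significant clinical events occurring over the past year: dates of onset and resolution, use of medical services, treatments, and resulting ongoing health concerns".
- Section 5.3 (Visit 2, HIV-positive cohorts): "Significant clinical events occurring over the past year: dates of onset and resolution, use of medical services, changes to antiretroviral and other medications".
- Section 7.1.2 (SAEs, after baseline): "Thereafter, at each yearly visit, SAEs occurring over the past year will be recorded".

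The health-care-use item at Visits 2 and 3 has the same limit. The year-1 telephone contact for HIV-negative participants (5.3a) does not: "Details of any changes in circumstances or illnesses and medication will be documented".

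On timing, section 2.0 has "Visit 2 (12 months after visit 1) HIV positive cohorts only", with Visit 3 at 24 months. Neither visit has a tolerance, although the plan does give limits elsewhere (60 days for screening, 30 days for the DXA scan). Section 5.6 puts recruitment in months 1–12, "with annual visits from months 13-24 (visit 2) and 25-36 (visit 3"). No section says what to ask when the previous contact was missed or is more than a year old.

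Section 8.1 defines incidence as the proportion of each cohort with a new or recurrent event during follow-up. Comparisons, where numbers allow, are by logistic or Poisson regression. No offset or covered-time denominator is stated.

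**The concern.** A one-year question asked at months 12 and 24 covers follow-up exactly, with no slack. If the year-1 contact is missed, or two visits fall more than a year apart, a site following the text will not ask about part of the participant's follow-up. Under section 8.1 that time still counts as follow-up.

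The first clinical objective in section 4.3 is the incidence of serious conditions in the three cohorts. Section 8.1 expects few of these events, so each loss matters for description, and an event that was never asked about cannot be reliably recovered at analysis. Section 8.4 makes participant retention something to monitor, so incomplete attendance is foreseen. The look-back is also worded differently by HIV status at year 1, which adds a possible difference in ascertainment between the groups being compared.

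**Working it through.** **The plan's own figures.** Section 8.1 expects at most 17 myocardial infarctions, 20 malignancies and 7 cases of liver failure in the HIV-positive groups combined. These cannot be reproduced because the underlying rates are not given. They serve here only as the counts that an incomplete look-back would affect.

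**Coverage for one participant.** Unasked time = follow-up to the last visit, minus the union of the 12-month periods before each attended visit (5.3, 5.4).

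| Year-1 contact | Visit 3 | Unasked | Share of follow-up |
|---|---|---|---|
| month 12 | month 24 | 0 of 24 | 0% |
| missed | month 24 | 12 of 24 (months 0–12) | 50% |
| missed | month 30 | 18 of 30 | 60% |
| month 15 (HIV-positive) | month 24 | 3 of 24 (months 0–3) | 12.5% |
| month 12 | month 27 | 3 of 27 (months 12–15) | 11% |

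The fourth row does not carry over to HIV-negative participants. Section 5.3a states no period, so a call at month 15 can cover months 0–15. The missed-contact and late-Visit 3 rows apply to all cohorts, because section 5.4 does.

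**Cohort level.** The documents give no missed-visit rate, so assume that a proportion p misses Visit 2 and attends Visit 3 at month 24. Assume also a constant event rate that is the same in those who attend and those who miss, and no recovery from any other source. The share of events unasked is then p × 12/24 = 0.5p.

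| p (assumed) | Share unasked | Of 17 MI | Of 20 malignancies | Of 7 liver failure |
|---|---|---|---|---|
| 5% | 2.5% | 0.4 | 0.5 | 0.2 |
| 10% | 5% | 0.9 | 1.0 | 0.4 |
| 20% | 10% | 1.7 | 2.0 | 0.7 |
| 30% | 15% | 2.6 | 3.0 | 1.1 |

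**Between cohorts.** The apparent HIV-positive to HIV-negative ratio is the true ratio multiplied by (1 − 0.5p₊)/(1 − 0.5p₋).

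- p₊ = 10%, p₋ = 20%: 0.95/0.90 = 1.056.
- p₊ = 10% to 30%, p₋ = 0: 0.95 to 0.85.

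The sign depends on the assumed split.

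**With a look-back to the last completed contact.** Unasked time is 0 in every row of the first table, provided that Visit 3 is attended.

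**The case against.** **On schedule, nothing is lost.** This is right: visits at 12 and 24 months leave no gap. A reader might take the year-wide blocks in section 5.6 as permission for visits up to 23 months apart. The text does not support that, because the blocks are consistent with study-calendar periods after twelve months of staggered recruitment. The point rests on the absence of a rule for a missed or late contact, not on section 5.6.

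**Not every item has the one-year limit.** This also stands. Section 5.3a has no period, fracture occurrence has none in its bullet, medications are recorded by start and stop dates, and the questionnaire asks about pain over the past month. A reader might apply the calculation to the 105 expected fractures and infer a loss of 5 to 8. The documents do not support this, because the fracture item does not carry the one-year limit. It refers to Appendix 1, where the visible falls question covers 28 days, a different matter.

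**Medical history is scheduled at every visit.** Section 2.0 does list it, but as defined by the protocol text. That leads back to 5.3 and 5.4; the full clinical history appears only at baseline (5.2).

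**Other sources would find the events.** In part. SAEs are reportable between visits, related or not: "An SAE form should be completed and faxed to ICTU for all SAEs within 24 hours of notification about the event". That depends on the site hearing of the event. Note review and GP/hospital contact exist, and HIV-negative participants must permit GP contact (4.1), but at the follow-up visits both sit within the one-year health-care item. The UK CHIC download (4.2) includes laboratory tests, which helps with renal disease. It does not list myocardial infarction, non-AIDS malignancy or fractures, and it covers clinic patients only. These sources reduce the loss but do not close the gap.

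**The analysis could handle it.** Onset dates are collected, so a Poisson model restricted to covered person-time would lose precision rather than be biased, provided that missed contacts are unrelated to events. Section 8.1 does not specify this, and its definition of incidence as a proportion over follow-up does the opposite.

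**Conclusion.** The point holds for clinical events and health-care use at Visit 2 (HIV-positive) and Visit 3 (all cohorts), and for yearly SAE recording. A missed year-1 contact followed by Visit 3 at month 24 leaves 50% of that participant's follow-up unasked; a Visit 3 three months late leaves 11%. For the cohort, an assumed 5–30% missing Visit 2 gives 2.5–15% of the events under these items unasked. This is a ceiling under the stated rate assumptions, before other sources recover any.

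Two stronger conclusions are tempting. One is that incidence will be undercounted. That requires missed or late contacts, events that no other source finds, and uncovered time left in the denominator; the documents establish only that the plan does not prevent this. The other is that the HIV-positive to HIV-negative ratio will be inflated by about 6%. That comes from one assumed split of missed contacts (10% v 20%), and other splits reverse the direction. The documents support neither a size nor a sign for between-cohort bias. The change is still worth making, because the gap arises at collection and is cheap to close there.

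**What to change.** - In 5.3, 5.4 and 7.1.2, replace the one-year look-back with the period since the last completed study contact (or since baseline if there was none) for clinical events, SAEs and health-care use.
- Add the same look-back to 5.3a, which now states none, so that all cohorts are asked about the same period.
- Pre-fill the date of the last completed contact on the eCRF.
- Express health-care use per person-year of the period covered, since that period will no longer always be one year.

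The cost is a wording change and one pre-filled date. The downside is recall over 24 months or more for the minority who missed a contact. The change does not help participants who never attend Visit 3; their time after the last completed contact stays unasked.
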